Initial screening: After phone consent, all potential participants will undergo an initial screening interview, via telephone or in-person depending on the recruitment setting (**Figure 7**). This screening procedure will include a knee OA screening interview that has shown 87% specificity and 92% sensitivity for detecting knee OA.⁸² This interview includes four questions regarding knee pain and swelling and previous diagnosis of knee OA. The initial screening will also assess MRI eligibility, age, gender, handedness, and additional health history information, and demographic information such as education level, household size and race/ethnicity for sample descriptive purposes. The Telephone Interview for Cognitive Status (**TICS**) will be given to participants to assess cognitive status. Eligible individuals will be scheduled for the Health Assessment Session. All participants will undergo the same procedures as described below, but control subjects will have the option to participate in acute (i.e., same day) oxytocin/placebo administration. If a control participant does not wish to undergo the spray administration, they would complete all other aspects of the visits. If control participants wish to undergo the spray administration, this will occur the same day as the neuroimaging visit (i.e., acute administration).

Phase One Procedures for Knee OA Participants:

Health Assessment Visits (Pre/Post)

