We will compensate control participants with up to \$330 upon study completion in the form of a pre-paid, reloadable VISA card issued by the University of Florida or by cash payments. In particular, for completion of

- Screening Visit, Baseline Visit: \$75
- Sensory Visit: \$75
- Neuroimaging Visits (up to 2 visits): \$75 per visit
- (Optional) extra \$30 if you choose to participate in the nasal spray treatment.

Power and sample size considerations: Based on our pilot study estimates, we plan to recruit 160 participants, i.e., 80 participants in each of the randomly assigned treatment groups for the baseline visits. Assuming an attrition rate of 20% at the follow-up visits, we will have 128 participants (64 in the OT and 64 in the P group) at the 4-week post-intervention follow-up visits. This sample size yields a power over 0.80, even based on a very conservative Bonferroni correction for multiple comparisons (i.e., testing twelve hypotheses), which lowers the alpha level from $\alpha=0.05$ to $\alpha=0.006$. However, our proposed data-analytic strategy will use the Benjamini and Hochberg procedure to control for multiple comparisons, which is less stringent than the Bonferroni correction, and thus we expect the actual power to be larger than 0.80.

Hypotheses and data-analytic strategy: We summarize all hypotheses and planned analyses in **Table 3 for aims 1 and 2.** The statistical analyses will be conducted by Co-I [name] (Biostatistician) in

Protocol: IRB201801467 (UCOPE Study)

IRB version: 10/1/2018

PI version: 05/10/2024

collaboration with [name] (Consultant, Institute on Aging Biostatistics and Bioinformatics Core Leader, see letter of support) using R software. For studying the relationship between pre- to post-intervention (longitudinal) outcomes and predictors, we will fit linear mixed effects models (**LMEMs**) [1] with subject specific random effects to account for the within-subject correlation, by R function “lmer”.¹⁰⁹ Baseline outcomes and covariates will be adjusted to take account for confounding effects. Below is the formula for the linear mixed effect model:

$$y_{ik} = \mu + \alpha_i + \beta \mathbb{I}(z_i = 1) + \sum_{l=0}^L \gamma_l x_{il} + \eta \mathbb{I}(k = 2) + \theta \mathbb{I}(z_i = 1, k = 2) + \varepsilon_{ik}, \alpha_i \sim N(0, \sigma_0^2), \varepsilon_{ik} \sim N(0, \sigma^2) \quad [1]$$

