where y_{ik} is the outcome variable (e.g., pain intensity/sensitivity/function for Aim 1) for subject i and visit k ($k = 1$ for intervention and $k = 2$ for post-intervention); μ is the intercept term; $\alpha_i \sim N(0, \sigma_0^2)$ is the random effect with variance term σ_0^2 for subject i ; z_i is the treatment indicator with $z_i = 0$ for P and $z_i = 1$ for OT, β is the treatment effect (OT effect compared to P effect) and $\mathbb{I}(\cdot)$ is the indicator function which equals 1 if the argument inside (\cdot) is true and equals 0 otherwise; x_{il} is the l^{th} covariates for subject i with $l = 0$ for baseline level (e.g. baseline pain intensity before treatment for Aim 1) and $l = 1, 2, \dots, L$ for L covariates (i.e., age, sex, race...); η is the time effect of post-intervention visit compared to pre-intervention visit; θ is the interaction effect between post-intervention and OT; $\varepsilon_{ik} \sim N(0, \sigma^2)$ is the error term with variance σ^2 . From equation [1], we will test whether there is a significant OT effect for both intervention and post-intervention. LMEMs allow for missing data if missing-at-random (MAR).

Table 3. Proposed hypotheses and planned analyses.

Specific Aims	Hypotheses	Planned Analyses
#1: Clinical and experimental pain	H1a: OT vs. P administration will reduce self-reported pain intensity	LMEMs* ; DV: Clinical pain IV: Treatment (OT/P)
	H1b: OT vs. P administration will decrease experimental pain sensitivity	LMEMs* ; DV: QST IV: Treatment (OT/P)
	H1c-1e: OT vs. P administration will increase physical, cognitive and emotional function	LMEMs* ; DV: SPPB, Exe. Function, Catastrophizing IV: Treatment (OT/P)
#2: Inflammatory mechanisms	H2a: OT vs. P will decrease systemic inflammation	LMEMs* ; DV: Plasma cytokines (IL6, TNF α , IL10) IV: Treatment (OT/P)
	H2b: OT vs. P will decrease brain metabolite concentrations associated with neuroinflammation	LMEMs* ; DV: Brain metabolites (tCr, MI, Cho) IV: Treatment (OT/P)
	H2c: Decrease in brain metabolites and systemic cytokines will be associated with decrease in clinical pain	Correlations/ Regressions IV: Decrease in brain metabolites and systemic cytokines DV: Decrease in clinical pain

Note. **IV** = Independent variable; **DV** = Dependent variable; **LMEMs**: linear mixed effects models; *Adjusted for baseline outcomes and covariates (age, sex, race, BMI, KL score, hip OA, plasma biomarkers).

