For **Aim 1**, the primary outcome will be self-reported pain, and plasma levels of OT as a modifier of a significant treatment (OT vs. P) response, using an intent-to-treat approach. Secondary outcomes include a standardized, multimodal experimental pain battery and physical, cognitive, and emotional functioning measures. For hypotheses **H1a** to **H1e**, we will use equation [1] to evaluate and test the effect of OT at 4-weeks post-intervention compared to P. Baseline outcomes and covariates (age, sex, race, hip OA, and inflammatory biomarkers) will be properly adjusted. A 50% reduction in self-reported pain intensity will demonstrate a clinically significant effect of OT compared to P. For **Aim 2**, the primary outcomes are proton MRS metabolites in frontal brain regions (tCr, MI, Cho) and plasma immune markers (IL-6, TNF- α , IL-10). For hypotheses **H2a** and **H2b**, we will use equation (1) to evaluate changes from baseline to post-intervention. Covariates (age, sex, race, hip OA) will be properly adjusted. For hypothesis **H2c**, we will use correlational tests and regression methods to evaluate the association between brain metabolites, systemic cytokines, and clinical pain to consider the inter-individual variability in treatment response. Consistent with IMMPACT recommendations we will perform a secondary analysis considering total number and amount of rescue medication doses in a matrix alongside pain relief, with higher scores assigned to those patients with high levels of relief and minimum rescue, and lower scores assigned to patients who have rescued the most and have lower pain relief scores.⁷⁷ For exploratory aim 3, similar strategies will be employed.

7. Possible Discomforts and Risks

Equipment used in this research meet all current safety standards, and all research staff will be highly trained in the use of all equipment. This study may include risks that are unknown at this time. Potential risks for this study are related to use of study product, neuroimaging, blood draw procedure, blood pressure measurement, the physical performance tests, the cognitive function tests, the sensory testing, and potential loss of confidentiality related to study participation, as discussed in detail below.

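### Equation [1] defines visit 1 both as intervention and as pre-intervention, so the coefficient labelled the treatment effect may be only a baseline difference, and no contrast is tied to any hypothesis

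*Combined protocol and SAP*

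**What the plan says.** All of this is in section 6, Research Plan. Under Hypotheses and data-analytic strategy, the model is introduced "For studying the relationship between pre- to post-intervention (longitudinal) outcomes and predictors". Its fixed part has a treatment term β, a baseline covariate x_i0, a second-visit term η and a treatment-by-second-visit term θ.

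The definitions below the equation set k = 1 to intervention and k = 2 to post-intervention. They then say that β "is the treatment effect (OT effect compared to P effect"), that x_i0 stands "for baseline level (e.g. baseline pain intensity before treatment for Aim 1"), and that η "is the time effect of post-intervention visit compared to pre-intervention visit". They close with "we will test whether there is a significant OT effect for both intervention and post-intervention".

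The text after Table 3 gives two verbal targets for the same equation. For H1a–H1e it is used "to evaluate and test the effect of OT at 4-weeks post-intervention compared to P". For H2a and H2b, "we will use equation (1) to evaluate changes from baseline to post-intervention".

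The schedule in the same section has a baseline set of sessions in each phase and one matching set in the last week of treatment. The assessment blocks carry headings such as "Health Assessment Visits (Pre/Post").

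**The concern.** The term η multiplies the indicator for k = 2, so its reference level is k = 1. Defining η against a pre-intervention visit makes k = 1 pre-treatment, which contradicts the explicit statement that k = 1 is intervention. This is the model for the primary pain outcome and for every mixed-model hypothesis in Table 3.

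Two things are at stake. First, the meaning of β and θ depends on the reading, and on one reading the coefficient named as the treatment effect contains no information about oxytocin. Second, if k = 1 is pre-treatment, the baseline score can be both an outcome (y_i1) and a covariate (x_i0). That upsets the standard error of the very contrast Aim 1 needs.

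**Working it through.** **Step 1. Which reading do the documents favour?**

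| Points to k = 1 pre-treatment | Points to k = 1 on treatment |
|---|---|
| Definition of η | Explicit definition of k |
| Model introduced for pre- to post-intervention outcomes | β labelled the treatment effect |
| Pre/Post headings on the health, sensory and neuroimaging visits | A separate pre-treatment covariate is listed |
| Verbal Descriptor Scale taken before and after treatment | Oxytocin effect tested at two time points |
| One assessment set in the last treatment week, none earlier on treatment | Smartwatch pain ratings during treatment (stated as planned under Real-time assessment, as optional under Intervention period) |

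The left column is stronger. No earlier on-treatment session is scheduled for the pain scale, sensory testing, physical performance, cognition, cytokines or spectroscopy. The smartwatch ratings keep the right column possible for self-reported pain only.

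**Step 2. What each coefficient means.** From the equation, oxytocin minus placebo is β at k = 1 and β+θ at k = 2.
- k = 1 pre-treatment: β is the pre-treatment arm difference (expected value zero under randomisation); θ is the effect on change.
- k = 1 on treatment: β is the on-treatment effect; θ is only the further change in that effect by visit 2.

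The Aim 1 target is β+θ on either reading. The Aim 2 target is θ if k = 1 is pre-treatment.

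This was illustrated by REML random-intercept fits with 64 v 64 (from Power and sample size considerations), SD 1, two-sided 5%, and a true effect of 0.5 SD. The effect and the pre–post correlation r = 0.3/0.5/0.7 are assumptions, since the documents give neither. The pre-treatment rows use the equation as printed with x_i0 = y_i1; the on-treatment rows assume the same effect at both visits.

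| Reading | Term | Rejects at r = 0.3/0.5/0.7 |
|---|---|---|
| Pre-treatment | β | 0/0/0% |
| Pre-treatment | θ | 73/85/96% |
| On treatment | β | 84/90/98% |
| On treatment | θ | 4.4/5.3/6.0% |

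**Step 3. Baseline as both outcome and covariate (k = 1 pre-treatment, x_i0 = y_i1, two-visit fit).** The covariate slope is truly 1 at visit 1 and r at visit 2, but the model fits one slope, (1+r)/2. The subject variance is estimated as zero in essentially every run, so one residual variance is pooled over the visits:
- visit 1 residual variance: (1−r)²/4
- visit 2 residual variance: (1−r)²/4 + 1 − r² = (1−r)(5+3r)/4
- pooled: (1−r)(3+r)/4

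At r = 0.5 these are 0.0625, 0.8125 and 0.4375. The standard error for β+θ should rest on 0.8125 but rests on 0.4375. The ratio of model SE to true SE is √[(3+r)/(5+3r)] for β+θ and √[(3+r)/4] for θ. Type I error is 2[1 − Φ(1.960 × ratio)].

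| r | Ratio, β+θ | Type I, β+θ | Ratio, θ | Type I, θ |
|---|---|---|---|---|
| 0.3 | 0.748 | 14.3% | 0.908 | 7.5% |
| 0.5 | 0.734 | 15.0% | 0.935 | 6.7% |
| 0.7 | 0.722 | 15.7% | 0.962 | 5.9% |

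Simulation of the same fit (6,000 runs per r) gives 15.0/15.5/16.8% for β+θ and 7.8/7.1/6.3% for θ.

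**Step 4. Dependence on the fit.** The design is a crossover, but neither the treatment indicator nor x_i0 has a period index, so which baseline enters is open. Type I error of β+θ at r = 0.3/0.5/0.7:

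| Fit | Type I error |
|---|---|
| Crossover, each period's own baseline | 13.3/14.7/15.8% |
| Crossover, single study-entry baseline | 5.2/5.5/5.1% |
| Same, cross-period correlation 0.2 lower | 6.0/6.0/7.2% |
| k = 1 on treatment | 4.9/4.9/4.9% |
| Pre-treatment k = 1, separate x_i0 correlated 0.9 with y_i1 | 12.0/11.7/10.6% |
| Same, correlated 0.8 | 9.5/9.3/6.4% |

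The crossover rows assume 64 per sequence.

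**The case against.** The strongest reply is that Aim 1 already has its target. Oxytocin against placebo at the post-intervention visit is β+θ however k = 1 is read, so the estimand for the primary pain outcome does not move. That stands. A reader might infer that the primary coefficient is free to be picked after the data are seen; the documents do not support so strong a claim, because the verbal target constrains the choice. What remains is that no contrast is written beside that target, that the definitions call β the treatment effect and promise tests at two time points, and that Aim 2 asks the same equation for change. Also, β and θ fully exchange roles only if the effect is equal at both visits.

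A second reply is that the printed covariate belongs to the subject, not the period. Carried into the crossover, that suggests one study-entry baseline and nearly nominal error. This also stands. A reader might infer that the planned analysis has a false-positive rate near 15%; the documents do not commit to the fit that produces it. Equally, they do not exclude it, since each phase has its own baseline visits.

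For Aim 2, the covariate list after Table 3 leaves out the baseline outcome, which would avoid double use, but the Table 3 footnote puts it back. The follow-up calls after the last phase do include a pain questionnaire. They come after both treatments have been given, however, and cover none of the sensory, performance, cytokine or spectroscopy outcomes.

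**Conclusion.** Wrong as written. The visit index contradicts itself within one set of definitions, and this needs no assumed figures. Pre-treatment is the better-supported reading, but it is not certain for self-reported pain. On that reading the label on β is wrong, and a test of β would say nothing about oxytocin.

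The second fault is conditional. It needs a pre-treatment k = 1, a covariate x_i0 that is the same measurement as y_i1 or closely correlated with it, and either the two-visit fit as printed or a crossover fit with own-period baselines. With the same measurement, type I error for the Aim 1 contrast is about 14–17% (13.3% at the lowest in the own-period crossover simulation) and about 6–8% for θ. Elsewhere it is about 5%, or up to about 7% with a study-entry baseline and lower cross-period correlation. These sizes rest on r = 0.3–0.7, equal variances and 64 per group or sequence.

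**What to change.** Change the analysis wording as follows.
- Define k by the scheduled visits.
- Give the treatment indicator and the baseline a period index.
- Use the pre-treatment score once. Either make the post-treatment score the outcome, with that period's pre-treatment score as covariate, inside the crossover model, and test the treatment coefficient (simulated type I error 5.3/5.5/5.0%). Or keep pre and post scores both as outcomes, drop x_i0, constrain the treatments to be equal at baseline and test θ (5.5/5.2/5.5%). The second option needs a covariance that lets within-period and between-period correlation differ; a single random intercept gives 6.0–6.8% if the cross-period correlation is 0.2 lower.
- Write one tested contrast beside each of H1a–H2b, and make the label for β and the two-time-point sentence agree with it.
- If an on-treatment k = 1 was intended, say which assessment supplies it and for which outcomes.

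The cost is text in the analysis section. No new data or visits are needed.

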Specific Aim 2: To characterize inflammatory mechanisms contributing to the inter-individual variability in analgesic response to OT. We will assess central and peripheral inflammatory processes using proton MRS in frontal brain regions and plasma immune markers, respectively. Based on our preliminary data, we hypothesize that compared to P, OT administration will result in significant: **H2a**) decrease in plasma levels of IL-6, TNF- α , and IL-10; and **H2b**) decrease in brain metabolite concentrations associated with inflammation (i.e., *MI*, Cr, Cho). Further, **H2c**) decrease in brain metabolites and systemic cytokines will be significantly associated with decrease in clinical pain intensity. Other markers of brain structure and function will also be significantly associated with changes in clinical pain intensity (**H2d**).

Exploratory Aim 3: To characterize effects of acute intranasal OT administration on clinical and experimental pain as well as underlying neurobiological mechanisms in younger and older controls. We will perform similar experiments as above in control participants to further understand OT's analgesic effects across the lifespan in the absence of knee OA pain. However, acute OT administration will be used in healthy controls versus chronic administration in the presence of Knee OA.

6. Research Plan

We propose a double-blinded, randomized cross-over design that will randomize older adults with symptomatic knee OA pain and/or back pain to four weeks of intranasal self-administration of either OT or P (48 IUs daily) followed by a four-week washout period and a second four weeks of intervention (either OT or P). Our study design was guided by recommendations by the IMMPACT group for clinical pain trials.⁷⁴⁻⁷⁷ After initial screening, eligible participants will undergo up to four baseline sessions (health, sensory, and neuroimaging) for collection of clinical, functional (physical, cognitive, emotional), QST, and brain imaging data lasting 2-3 hours. At some point during the baseline, intervention, and post-intervention periods, participants may wear a Samsung Gear S[®] or Apple smartwatch or Oura ring to obtain daily pain, mood, and social activity assessments and to objectively measure physical activity levels and sleep quality. During the intervention, participants will self-administer twice daily 24 IUs

Protocol: IRB201801467 (UCOPE Study)

IRB version: 10/1/2018

PI version: 05/10/2024

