(e.g., for osmolality levels, sodium levels, and any other blood markers out of range) to ensure that no adverse changes have occurred during the study intervention. Additionally, before and after the intervention period participant will fill out the Goal Attainment Scale (**GAS**). For the majority of the 4-week intervention periods, participants may complete daily assessments via their Samsung Gear S® or Apple smartwatch or Oura Ring. We will be able to assess pain, mood, and activities at random times throughout the day. Participants will be contacted once a week to assess side effects and asked if they have been completing their diaries. Any symptom reported as moderate or severe will be brought to the PIs' attention and will be discussed with the study MD as needed on a case by case basis. These weekly calls will also ensure regimen compliance and will assist participants in download of the Samsung Gear S® or Apple smartwatch or Oura Ring data to a secure research server. We have successfully established a similar approach in other projects within our institute, and the DSAT Core has validated pipelines for data analysis.^{92,106}

Post-Intervention Assessments for Knee OA Participants

In the last week of the intervention, participants will be scheduled to return for up to four (or 6 with the MRI) post-intervention visits, which will be identical (with minor exceptions) to the baseline visits. Importantly, at the follow-up Health Assessment we will assess changes in health status, and their global impression of change (**PGIC/MPIC**) since starting the intervention.

Wash-out Period for Knee OA Participants

Participants will undergo a four-week wash-out period in between phases one and two. The wash-out period will serve to prevent confounding variables between both drug administrations. Four weeks is a sufficient period of time for participants to return to baseline levels prior to drug administration.

Phase Two Procedures for Knee OA Participants

After the four-week wash-out period, participants will enter phase two of the study. Phase Two is completely identical to Phase One: up to 4 (or 6 with the MRI) Baseline Visits, Intervention Period, and up to 4 (or 6 with the MRI) Post-Intervention Visits. Participants will be given the other drug from the first intervention period per randomization.

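### H2c names no OT-versus-placebo contrast, so person-level change common to both phases could be read as an OT mechanism

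*Combined protocol and SAP*

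**What the plan says.** In Section 5, Aim 2 is to "characterize inflammatory mechanisms contributing to the inter-individual variability in analgesic response to OT". H2c, placed under it, states that "decrease in brain metabolites and systemic cytokines will be significantly associated with decrease in clinical pain intensity", with no comparison against placebo in that hypothesis.

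In Section 6, Table 3 gives the H2c method as correlations or regressions with "IV: Decrease in brain metabolites and systemic cytokines DV: Decrease in clinical pain". The five other rows (H1a, H1b, H1c-1e, H2a, H2b) all name treatment as the independent variable. The footnoted covariate adjustment is attached to the mixed-model rows only.

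The text after Table 3 repeats that "we will use correlational tests and regression methods to evaluate the association between brain metabolites, systemic cytokines, and clinical pain" and adds a purpose, "to consider the inter-individual variability in treatment response". For H2a and H2b the same paragraph uses equation [1] "to evaluate changes from baseline to post-intervention", which is the only definition of change given for these markers. Equation [1] gives each subject a single treatment indicator and has no period or sequence term.

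The design is a two-period crossover. Phase Two repeats the baseline and post-intervention visits, and "Participants will be given the other drug from the first intervention period per randomization".

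**The concern.** Aim 2 asks why people differ in their response to OT. In this crossover, a completer's response to OT can be calculated as the change in the OT phase minus the change in the placebo phase. H2c does not ask for that quantity and does not bring treatment into the model in any other way.

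If the decreases are taken from the OT phase alone, each one contains whatever that person would also have shown on placebo: natural course, regression to the mean and placebo response. People who tend to improve on everything would then create a marker-pain correlation that has nothing to do with OT. If both phases are combined as ordinary rows, the same problem remains and each person is counted twice. In either case a significant H2c result could be reported as an inflammatory mechanism of OT analgesia when it is not specific to OT.

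**Working it through.** **The plan's own figures.** No effect size, correlation or power is given for H2c. The sample size section gives 160 enrolled and 20% attrition: 160 x 0.80 = 128. I take n = 128 people with both phases, which is generous for the metabolites because the Compensation section makes MRI optional.

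**Model (assumed, not in the documents).** OT has no effect on marker or pain. Each standardised change is a person-level part common to both phases (share h of the variance, marker-pain correlation g) plus a phase-specific part (share 1 - h, marker-pain correlation c). Then:

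- correlation within the OT phase = h x g + (1 - h) x c
- correlation of the OT-minus-placebo differences = c, because the common part cancels
- chance of significance at two-sided 0.05, with x = sqrt(n - 3) x atanh(correlation): Phi(x - 1.96) + Phi(-x - 1.96), where sqrt(125) = 11.18

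**Case c = 0.** Worked example for h = g = 0.5: correlation 0.25, atanh = 0.2554, x = 2.856, Phi(0.896) = 0.815. For h = 0.1, g = 0.3: correlation 0.03, x = 0.335, Phi(-1.625) + Phi(-2.295) = 0.063. Simulated results agree:

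| h | g | OT-phase correlation (h x g) | OT phase significant | both phases as independent rows | OT minus placebo |
|---|---|---|---|---|---|
| 0.1 | 0.3 | 0.03 | 6% | not run | not run |
| 0.2 | 0.2 | 0.04 | 7.5% | not run | not run |
| 0.25 | 0.3 | 0.075 | 13.5% | 23% | 4.8% |
| 0.5 | 0.3 | 0.15 | 39% | 65% | 5.0% |
| 0.5 | 0.5 | 0.25 | 82% | 97% | 5.0% |
| 0.75 | 0.5 | 0.375 | 99% | over 99% | 4.7% |

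Combining phases as independent rows overstates significance even when g = 0: 7.9% at h = 0.5 and 11.4% at h = 0.75. With n = 64 and h = g = 0.5, the OT-phase figure is 52%, against 5.1% for the difference.

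**A second route, if OT and placebo records (64 + 64) are combined without a treatment term.** Suppose OT shifts both means by s SD with no individual link. The correlation is then (s^2/4) / (1 + s^2/4). For s = 0.5 this is 0.0625/1.0625 = 0.059, and for s = 0.8 it is 0.16/1.16 = 0.138. The simulated false-positive rates are 10% and 35%, and they return to 5% once treatment is in the model.

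**Limit of the difference score (c > 0).** Its correlation is c, so at n = 128 the formula gives:

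- c = 0.1: x = 1.122, 20%
- c = 0.2: x = 2.267, 62%
- c = 0.3: x = 3.460, 93%

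Simulating the regression of differences with sequence and mean marker change included (h = g = 0.3) gave 19%, 61% and 94%. The difference score therefore removes change common to both phases. It does not remove co-movement within a phase that is unrelated to OT.

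**Why a slope comparison adds something.** In this model the marker-pain slope is h x g + (1 - h) x c in the OT phase and the same in the placebo phase. With no OT-specific link, the expected slope difference is therefore zero whatever c is.

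**The case against.** - **The plan does not say it will use raw change.** A reader might infer that H2c deliberately correlates pre-post decreases in place of OT-minus-placebo responses. The documents do not support that. The word decrease is left undefined for H2c, the stated purpose refers to treatment response, the Aim 1 text glosses treatment as OT against placebo, and regression methods could include a treatment term. This stands: the defect is an unspecified contrast, and pre-post change is only the plain reading. But the purpose is never carried into a variable, and Table 3, which names the variables, omits treatment in this row alone.
- **H1a, H2a and H2b already compare OT with placebo.** They do, and they would limit what is claimed. They test mean differences in pain and markers, not whether the link between an individual's marker change and pain change is specific to OT.
- **The percentages depend on invented inputs and an unadjusted test.** This also stands. At small shares the rate is close to nominal. The plan intends Benjamini-Hochberg control. At its stricter Bonferroni benchmark of 0.006, h = g = 0.3 falls from about 18% to 4.1% and h = g = 0.5 from 82% to 54%. Those rates still compare with a nominal 0.6%.
- **Difference scores are no cure.** Correct where phase-specific co-movement exists, as shown above. That limits what the repair proves; the current wording gives no protection against it either.
- **H2c is only associational.** It is nevertheless a numbered hypothesis under a specific aim, predicting a significant association. The exploratory work is Aim 3.

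**Conclusion.** The point holds in this form: H2c specifies no OT-versus-placebo contrast, does not say which phase or phases supply the decreases, and does not say how two records per person are treated. Following the Table 3 row as written would not isolate an OT-specific link, although the crossover with a baseline in each phase allows a better analysis of data already being collected.

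The direction needs only a positive marker-pain correlation in the person-level change common to both phases. The size is illustrative: about 6% false positives at h = 0.1, g = 0.3 and about 82% at h = g = 0.5, for n = 128, c = 0 and unadjusted 0.05. These are not estimates of this trial's error rate.

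A reader might also infer that an OT-minus-placebo correlation would establish mediation. It would not, because co-movement within a phase can produce it. The matter should be settled before analysis. It concerns the individual-response part of Aim 2 and leaves the primary pain comparison untouched.

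**What to change.** Rewrite H2c in Table 3 and the accompanying text as follows.

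1. Define the change for each phase, from that phase's own baseline to its post-intervention visit, for pain and for each marker.
2. Regress each person's OT-minus-placebo difference in pain change on the OT-minus-placebo difference in each marker's change, adjusting for sequence and for the person's mean marker change over the two phases. The sequence term matters because entry requires raised pain and raised IL-6, so regression to the mean is likely to fall mainly in the first phase.
3. Test whether the marker-pain slope differs between OT and placebo phases: a model on both phases with a treatment-by-marker-change term, a period term, and the within-person correlation accounted for. Claim an OT-specific mechanism only in the light of this comparison.
4. Present phase-specific correlations as descriptive.

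The cost is wording in the analysis plan and no new data. The limits should be stated with it. Difference scores are noisier. Only people who complete both phases contribute to step 2, and fewer for metabolites because MRI is optional. The association in step 2 alone is not proof of mediation. Nor would a null result in step 3 exclude OT acting along a marker-pain relation that also exists under placebo.
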